### **Procedures:**

All participants will be administered an IRB-approved pre-consent telephone screen, which will inquire about the inclusion/exclusion criteria, including PD diagnosis, prior neuropsychological testing, cognitive/dementia diagnosis, and mobility. In the case of an outside referral, a release of information (ROI) may be obtained to confirm the PD diagnosis or other inclusion/exclusion uncertainties. Additionally for outside referrals, we will attempt to minimize patient and provider burden by utilizing existing medical records pertaining to the PD diagnosis (neurological evaluation), with the patient's consent. Individuals who report any previous neuropsychological testing with a subsequent clinical diagnosis of dementia and/or a clinically-obtained MoCA scores below cut off will be excluded. These pre-consent screening questions are implemented to minimize patient burden by limiting the potential for exclusion prior to consent.

The majority of the potential participants who meet the above inclusion criteria (e.g., PD diagnosis, MoCA  $>20$  or clinical diagnosis of dementia, able to walk/stand without dependence on assistive device) will be referred by our Consultant, [name] (UCSD), who is a movement disorder specialist and neurologist. All participants will be administered an IRB-approved pre-consent telephone screen, which will inquire about the aforementioned inclusion and exclusion criteria, including PD diagnosis, prior neuropsychological testing, cognitive/dementia diagnosis, and mobility. These pre-consent screening questions are implemented to minimize patient burden by limiting the potential for exclusion prior to consent and testing.

### Assessments and Intervention

Upon consent, all potential participants will be administered a health/medical history questionnaire, MoCA, and BDI-II to screen for and confirm inclusion/exclusion criteria. Due to our pre-consent screening procedures, we anticipate that exclusion will be low at this point. However, those who do not meet criteria will be thanked and paid in full for the session. During consenting, the research study personnel will read the informed consent to the participants while they follow along with their own copy. Participants will receive a thorough explanation of the study and study personnel will answer participant questions as they arise. Participants will be administered a decisional capacity assessment to ensure that they understand all parts of the study. If they cannot answer the questions during the assessment the form will be read to them again and the questions will be re-administered. At that point in time, if he/she cannot answer the questions they will be thanked for their time and given referrals as needed. We do not plan on enrolling individuals who are unable to consent (dementia diagnosis is an exclusion) and we will not be requesting any waivers for written informed consent.

Those who meet criteria will be administered the pre-intervention neuropsychological battery within approximately one week prior to beginning the group by an examiner who will be blinded to group assignment. Participants will be group randomized to one of two 8-week conditions (i.e., 6-8 participants assigned in groups via R randomizer to either Mindfulness Based Stress Reduction (MBSR) or Psychoeducational Supportive Care). All activities will be conducted on the VA San Diego campus. MBSR and Psychoeducational Supportive Care groups will each consist of approximately 6-8 individuals with PD and be led by a trained instructor who is not involved in the clinical care or assessment of these participants. Participants will meet in groups for 2.5 hours once per week for eight weeks, with a 2.5 hour session ("retreat") between weeks 6 and 7. Each week and at the start of group, all participants will complete a brief form regarding changes in mood and medications. Any changes in mood will be addressed by clinicians on the protocol to assess for SI (please see MCM 11-24 Suicidality attached to protocol). We will offer assistance during each session to escort those who are at risk for falling (i.e., UPDRS fall item #13 > 0) to the bathroom and to and from their vehicle as appropriate.

All participants will be administered a battery of neuropsychological tests to measure HRQoL, cognition (e.g., executive function, attention, memory), and mood (i.e., anxiety, depression, and apathy), as well as motor symptoms, disease severity, and mindfulness engagement/practice. The UPDRS Part-III/Hoehn and Yahr Score (HYRS), which assess level of motor function and characterizes disease severity, will also be administered by study staff, certified in UPDRS administration, at their baseline assessment. If we are unable to obtain this score, we will obtain a ROI to access their UPDRS exam score(s) and HYRS. Tests will be administered at baseline, 8 weeks (post-treatment), and 6- and 12-months (follow-up assessments). Breaks will be offered and given during the assessment as needed. Study questionnaires are attached to the protocol submission.

Following the intervention and 6- and 12-months post-intervention, PD participants will be re-tested by a group-blinded research assistant. The UPDRS Part-III/HYRS will also be administered by study staff, certified in UPDRS administration, at the 12-month follow up appointment as well. Total participation time is 2-3 hours per session x 4 total sessions (-pre, -post, -6, and -12 month follow up). To better retain participants throughout the 12-month trial period, we will implement friendly reminder calls at 2-months and 1-month prior to each testing session as well as send a reminder letter with pertinent information (e.g., directions) 2-3 weeks prior to their appointment. In addition, MBSR will be offered to the Psycheducational Supportive group participants upon study completion.

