## Section 5 - Lay Language Summary

5) Provide a summary or synopsis of the proposed study using non-technical language (not more than 1 paragraph)

The overall aim of this longitudinal RCT is to determine the efficacy of MBSR to improve HRQoL, cognition, and mood, as well as to determine the longevity of the treatment response in individuals with PD. We hypothesize that HRQoL, cognition (particularly executive function), and mood (particularly anxiety) symptoms (will improve in PD participants following eight weeks of MBSR compared to PD participants randomized to an eight-week active Psychoeducational control condition. We further hypothesize that benefits of MBSR treatment will be evident at the 6- and 12-month assessments, such that those completing the MBSR group will demonstrate better HRQoL, cognition, and mood relative to those PD patients who completed the Psychoeducational Supportive Care (PSC) group. Potential mediators/moderators of the treatment response will be examined in exploratory hypotheses. Eighty-eight non-demented individuals with PD will be recruited and enrolled in the proposed study. Over-recruitment by 10% will be instituted to account for subject attrition or unusable data, and to ensure an adequately-powered sample size of 80 (40 per group). Participants will be randomized into either eight weeks of MBSR (n = 44) or eight weeks of PSC (n = 44). All participants will be administered a battery of neuropsychological tests to measure HRQoL, cognition (e.g., executive function, attention, memory), and mood (i.e., anxiety, depression, and apathy), as well as motor symptoms, disease severity, and mindfulness engagement/practice. Tests will be administered at baseline, 8 weeks (post-treatment), and 6- and 12-months (follow-up assessments) by an examiner blinded to group assignment. Data will be primarily analyzed using linear and multivariable random effects modeling. Findings from this study will provide critical information regarding the efficacy of MBSR for HRQoL, cognition, and mood in PD. Furthermore, results will

provide essential data regarding the long-term benefits of MBSR in PD, and elucidate potential mediators/moderators of treatment response.

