## Section 6 - Specific Aims

### 6) Provide a statement of specific aims and hypotheses that serve as the basis for this protocol. Emphasize those aspects that justify the use of human subjects.

Aim 1. To investigate the efficacy of MBSR to improve health-related quality of life in PD. Hypotheses: PD patients who complete MBSR will demonstrate (Primary Hypothesis 1a) greater improvement in HRQoL from baseline to post-treatment compared to PD participants randomized to a duration- and frequency-matched psychoeducational/supportive care control group; and (Hypotheses 1b) better HRQoL at the 6- and 12-month follow-up evaluations.

Aim 2. To examine the efficacy of MBSR to improve cognition in PD.

Hypotheses: PD patients who complete MBSR will demonstrate (Hypothesis 2a) greater improvement in cognition from baseline to post-treatment compared to PD participants randomized to a duration- and frequency-matched psychoeducational/supportive care control group, and (Hypotheses 2b) better cognition at the 6- and 12-month follow-up evaluations.

Aim 3. To determine the efficacy of MBSR in reducing mood symptoms in PD.

Hypotheses: PD patients who complete MBSR will demonstrate (Hypothesis 3a) greater improvement in mood from baseline to post-treatment compared to PD participants randomized to a duration- and frequency-matched psychoeducational/supportive care control group, and (Hypotheses 3b) better mood at the 6- and 12-month follow-up evaluations.

Exploratory Aim: To examine the mediators and moderators of treatment response on HRQoL following MBSR in PD. As cognitive and mood symptoms are associated with poor HRQoL in PD, we hypothesize that HRQoL change will be mediated and/or moderated by changes in cognition and mood from pre- to post-intervention. We will test the possible moderation/mediation effects of non-motor and motor symptoms on HRQoL following MBSR at 8 weeks (post-treatment), and 6- and 12 months.

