### Data Analysis

Data will be primarily analyzed using linear and multivariable random effects modeling.

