## Section 9.11 Pictures and Audio/Video Recordings of Patients

**9.11) Describe the purpose of photographs (facial), or audio, or video recordings of patients. Describe whether the recordings will contain, or potentially contain, identifiers. *Note: use of photographs or recordings must be covered in the informed consent process and documented consent documents (e.g., consent form, information sheets, telephone screen scripts).***

All sessions of MBSR and Psychoeducation/ Supportive Care will be audiotaped and available for rating in order to ensure fidelity and integrity of the protocol administration. All first sessions and a random sample of 10% of the audiotapes for the MBSR intervention will be reviewed by supervisors. [name] will also aid in the fidelity checks for the Psychoeducation intervention. Group facilitators will be provided corrective feedback, if needed. The facilitator will monitor attendance and note individual level of participation. Audio recordings will be destroyed at the end of the study. Audio recordings transferred into a computer system will be assigned group numbers and will not be individually identifiable. The key that relates the group numbers to the individuals will be stored separately, protected by strong passwords, and accessible only by approved study personnel. Recording members refer to each other by first name only, to ensure that they remain unidentifiable. Credibility, expectancy, engagement, practice, and facilitator competency will be examined in analyses.

We will also be video recording some of the group sessions. If 100% of group members agree to be recorded, we may video-record their group. If some of the subjects decline to be videotaped then we will not proceed with recording their session. Study participants may agree to such voluntary recording, or not, without any effect on the rest of their participation in the study.

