**12.1c) A master list of all VA subjects consented (written or not) under this protocol will be maintained.**

Agree  Disagree

**12.1d) Identify the circumstances under which consent will be obtained including where the process will take place; any waiting period between describing the research and obtaining consent including sufficient time for the prospective participant to consider participation, and any steps taken to minimize the possibility of coercion or undue influence.**

Informed consent will be obtained at the time of initial visit and the baseline (pre-intervention) evaluation will be conducted.

All potential participants will call or meet with a member of the research team who will explain the study's purpose and answer any questions. If the individual expresses interest in the study, they will be pre-screened to determine eligibility (e.g., PD diagnosis, history of dementia, mobility). If pre-screening eligibility is adequate for inclusion, they will be consented and the baseline (pre-intervention) evaluation will be conducted.

During consenting, the research study personnel will read the informed consent to the participants while they follow along with their own copy. Participants will receive a thorough explanation of the nature of the intervention, how participants will be randomly assigned to one of the intervention groups, their study involvement duration, compensation for their participation, possible risks and benefits, and potential alternative treatments. Study personnel will answer participant questions as they arise. Additionally, participants will be administered a decisional capacity assessment to ensure that they understand all parts of the study. If they cannot answer the questions during the assessment the form will be read to them again and the questions will be re-administered. At that point in time, if he/she cannot answer the questions they will be thanked for their time and given referrals as needed. We do not plan on enrolling individuals who are unable to consent (dementia diagnosis is an exclusion) and we will not be requesting any waivers for written informed consent.

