Given the age and medical condition (i.e., Parkinson's disease) of the participants, it is possible that individuals may experience medical or psychological changes unrelated to the study that would necessitate early termination of the study. If the individual situation warrants, participants may be able to rejoin a later group. Because both interventions (Psychoeducation/Supportive Care and MBSR) are not group therapy, there is no requirement that individuals will share personal and/or mental-health information. However, should any information be conveyed that causes study staff to be concerned about that participant's psychological well-being, appropriate referrals to the VA Geropsychiatry Clinic may be provided to veterans, or other appropriate community resources for veterans and non-veterans will be provided.

Due to the fall risk associated with individuals with PD, we will use the baseline MDS-UPDRS falling item (#13) in which a history of falls is categorized on a Likert scale from 0 (none) to 4 (falls >once per day). A history of falls as assessed by the MDS-UPDRS appears to be one of the best predictive methods of subsequent falls at this time. Those individuals who endorse a history of falling or score >0 on the MDS-UPDRS falling item, will be closely monitored. Should an individual who is at risk for falling be identified, we will offer assistance during each class to escort the individual to and from the intervention room, from their vehicle, as well as to and from the bathroom, if needed. As standard in MBSR, all participants will be encouraged to work within their own personal limits and preferences. Alternatives to the standard exercises will be offered. These alternatives include sitting in a chair in lieu of floor exercises; lying down for standing exercises; omitting certain (e.g., walking) meditations; and/or visualizing the movements in lieu of acting them out. These options are standard in MBSR and have also been implemented in other trials of MBSR for PD.

Suicidal ideation (SI) will be assessed by Beck Depression Inventory (BDI-II) item #9 at each assessment (i.e., pre-, post-, 6- and 12-months). Should an individual indicate  $\geq 1$  on the BDI-II item 9, the tester will immediately notify a licensed clinician on the protocol. The clinician will

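### Sets of 6-8 people are randomised and treated together, yet neither the analysis plan nor the sample size allows for the groups; ignoring them puts type I error at about 6-12% for an assumed ICC of 0.01-0.10

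*Combined protocol and SAP*

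**What the plan says.** - **Allocation and delivery.** Section 9, Assessments and Intervention: "Participants will be group randomized to one of two 8-week conditions (i.e., 6-8 participants assigned in groups via R randomizer". Each set then meets weekly for eight weeks, plus a retreat, under a trained instructor.
- **Other descriptions of allocation.** Section 5: "Participants will be randomized into either eight weeks of MBSR (n = 44) or eight weeks of PSC (n = 44". Section 12.1d says consent will explain "how participants will be randomly assigned to one of the intervention groups". Both can be read as allocation of individuals.
- **Sample size.** Sections 5 and 10 over-recruit by 10% "to ensure an adequately-powered sample size of 80 (40 per group"). No alpha, power, target effect, ICC or design effect is given.
- **Analysis.** The whole Data Analysis section reads: "Data will be primarily analyzed using linear and multivariable random effects modeling". It does not say what the random effects are for.
- **Primary hypothesis.** Section 6: "Primary Hypothesis 1a) greater improvement in HRQoL from baseline to post-treatment", that is, a comparison of change.
- **Group membership.** Section 15: "If the individual situation warrants, participants may be able to rejoin a later group". No rule says in which group such a person is analysed.

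**The concern.** If sets of 6-8 are allocated as blocks, the trial has roughly 12-14 randomised units, not 80. People in one group share an instructor, sessions and one another's company, so their outcomes are likely to be somewhat correlated. An analysis that treats them as independent understates the standard error of the arm contrast whenever that correlation is positive, and false positives rise.

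The one-sentence plan does not rule out a group effect. With four visits per person, however, a participant random effect is a natural reading, and it deals with repeated measures rather than with the randomised unit. A plan that fits both a valid and an invalid primary test has not fixed the test.

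The obvious repair can also miss. Hypothesis 1a concerns change from baseline. A group intercept that is constant over visits drops out of every difference between visits, so adding it leaves the standard error of the change contrast as it was.

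**Working it through.** **Inputs from the documents:** 44 enrolled and 40 analysable per arm (Sections 5 and 10); groups of 6-8 (Section 9); pilot HRQoL d' = 1.14 from 8 v 12 people (Section 7). **Assumed because not given:** two-sided alpha 0.05, 80% power, ICC 0.01-0.10.

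**1. The plan's own figure.** 80 x 1.10 = 88, so enrolment follows from 80 plus 10%. The 80 itself cannot be reproduced. At d' = 1.14 the usual formula gives 2(1.96 + 0.84)²/1.14² = 12.1, or 13 per arm. As a benchmark, 40 independent people per arm have 80% power for d = 0.634.

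**2. Number of groups.** 44/8 = 5.5 and 44/6 = 7.3, so K = 6 or 7 groups per arm, with 2K - 2 = 10 or 12 degrees of freedom for the arm contrast.

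**3. Design effect and type I error if groups are ignored.** DE = 1 + (40/K - 1) x ICC, and error ≈ 2[1 - Φ(1.96/√DE)]. For K = 6 and ICC 0.10, DE = 1 + 5.67 x 0.10 = 1.57, 1.96/√1.57 = 1.57, and the error is 11.7%. The simulated column is an ordinary t-test in 40,000 simulated trials per cell.

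**4. Detectable effect if groups are modelled.** Noncentral t on 2K - 2 df with variance inflated by DE.

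| K | ICC | DE | Error, formula | Error, simulated | Detectable d | Ratio to 0.634 |
|---|---|---|---|---|---|---|
| 6 | 0.01 | 1.06 | 5.7% | 5.7% | 0.715 | 1.13 |
| 6 | 0.05 | 1.28 | 8.4% | 8.2% | 0.788 | 1.24 |
| 6 | 0.10 | 1.57 | 11.7% | 12.0% | 0.870 | 1.37 |
| 7 | 0.01 | 1.05 | 5.5% | 5.6% | 0.699 | 1.10 |
| 7 | 0.05 | 1.24 | 7.8% | 7.9% | 0.759 | 1.20 |
| 7 | 0.10 | 1.47 | 10.6% | 10.8% | 0.828 | 1.31 |

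The error doubles only at an ICC of about 0.07 (K = 6) or 0.09 (K = 7); the simulated value was 9.9% in each case. Groups of exactly 8 give up to 13.3% at ICC 0.10 (DE = 1 + 7 x 0.10 = 1.70).

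Part of the rise in detectable d comes from the degrees of freedom alone. At ICC 0 it is already 0.695 (K = 6) or 0.683 (K = 7).

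**5. Baseline adjustment.** Multiply by √(1 - r²), assuming the same ICC range for the adjusted outcome. For K = 6, detectable d is 0.62-0.75 against 0.55 at an assumed r = 0.5, and 0.43-0.52 against 0.38 at r = 0.8.

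**6. The intercept-only model.** If an outcome is group effect + participant effect + error, both effects cancel from 8 weeks minus baseline. In three simulated two-visit data sets (K = 6, ICC of change 0.10), a model with group and participant intercepts gave the same standard errors as an unclustered t-test on change: 0.1914, 0.2247 and 0.2380 for both.

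**7. Tests that hold their level.** In the simulations a t-test on group means kept the error at 4.7-5.1%, as did a model with an unbounded group variance on 2K - 2 df. The bound matters because the estimated group variance was zero or negative in 17% (ICC 0.10) to 49% (ICC 0.01) of trials. Software that truncates it at zero then drops the group effect.

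**8. Power at the pilot effect.** At d = 1.14 with groups modelled, power is 0.955-0.995. If d' is an ordinary two-sample d from independent people, its 95% CI with 8 and 12 is about 0.16 to 2.09.

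**The case against.** - **The harm is conditional.** Random effects modelling may be meant to include a group effect, and the ICC is assumed. Both points stand: the established defect is that the group term is not stated, and at ICC 0.01 the error is only 5.6-5.7%. The primary test is still not fixed.
- **The allocation texts may not conflict.** Sections 5 and 12.1d are general descriptions, and only Section 9 gives the mechanism. That is a fair reading, and it makes block allocation the likelier design. If allocation proved to be individual, shared delivery would still induce clustering.
- **An intercept can suffice.** This is true when baseline is a covariate. The cancellation applies to raw change and arm-by-visit contrasts, and Section 6 does not fix which model is used. The numerical check used two visits, not four, but a constant intercept cancels from any difference between visits.
- **Power is ample at the pilot effect.** It is, so inadequate power is not shown. The pilot estimate is very imprecise, however, and high power does not protect the error rate.
- **The df method is a choice.** Other small-sample methods are defensible. What is needed is one that respects the small number of groups.
- **Rejoining.** Analysis in the original group follows from intention to treat. The group actually attended also matters for delivery effects and can be examined as a sensitivity analysis.

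**Conclusion.** The concern holds. The design on its plain wording randomises and treats sets of 6-8, and nothing in the documents carries this into the analysis or the sample size.

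If groups are ignored, the nominal 5% test of Hypothesis 1a has a true error of about 6-12%. If they are modelled, the detectable effect is 10-37% larger than for 40 independent people per arm, and an effect with 80% power under independence has about 53-72%. These figures rest on an assumed ICC of 0.01-0.10, two-sided alpha of 0.05, 6-7 groups per arm and 40 analysable per arm. The omission itself is certain; the size of the harm depends on the ICC. Whether 80 is adequate cannot be verified from the documents.

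**What to change.** 1. **Section 9:** state whether the set of 6-8 is the randomised unit, and make Sections 5 and 12.1d agree.
2. **Data Analysis:** specify participant and intervention-group random effects, with the group effect acting on the outcome after baseline. Use either a group-by-visit random effect, or baseline as a covariate with a group random intercept. Leave the group variance unbounded and test the arm contrast on number of groups minus 2 df (or Kenward-Roger with an unbounded group variance). Name a t-test on group-mean change as the check.
3. **Rejoining (Section 15):** analyse anyone who joins a later group in the group to which they were originally randomised.
4. **Sections 5 and 10:** replace the bare claim of adequate power with the detectable effect, alpha and power over a stated, assumed ICC range, and say whether baseline adjustment is included.

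Fix these before outcome data are analysed.

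**Cost.** Wording and model terms only; no new patients or visits. Section 9.11 already provides a link for the recordings: "The key that relates the group numbers to the individuals will be stored separately". The group number must still be carried into the analysis data. It is not among the REDCap variables listed in Section 27.2c1, and data shared for analysis under Section 27.3e1 would need it too. The statistical price is fewer degrees of freedom, a less favourable stated detectable effect, and a group variance that may be estimated as negative.
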